Participating parent and child weight will be measured at each major assessment (at baseline and every 6 months), and weight will be assessed throughout FBT as part of a goal setting and reinforcement system by the blind assessors. *Child height will also be measured at each major assessment or as needed to determine progress (This change was made on 11.9.17 prior to review and approval by the DSMB, DSMB approved protocol addenda on 11.2.18)*. Weight will be measured using a wireless, portable scale (SR Scales, Tonawanda NY), calibration certified. Two weights for each participant will be taken according to a uniform protocol and will be written on hard copy measurement sheets. The handwritten weights will be manually entered into the REDCap database by a blinded measurement coach, which will

eliminate potential measurement bias and minimize errors in data entry (*DSMB approved change, 11.18.19*). Height will be measured using the portable stadiometer HM200P PortStad by the Charder manufacturing company within the pediatric practices (This change was made on 4.6.17 prior to review and approval by the DSMB, DSMB approved protocol addenda on 11.2.18). Hard copy height and weight measurement forms will be uploaded to the secure REDCap database to allow the CCC, DCC and TFC to check for transcription and/or unit of measurement errors. All assessors will be provided with the height and weight protocol (see Height and Weight Measurement in **Appendix C**) in order to ensure that participants are being measured accurately and consistently and we will retain the written record of participant height and weight, as well. On the basis of height and weight, BMI is calculated according to the following formula: $BMI = kg/m^2$. Children will be considered overweight at or above the 85th BMI percentile for their age and sex.³⁵ Parents will be considered overweight if their BMI is greater than or equal to 25 kg/m^2 , and obese if their BMI is greater than or equal to 30.³⁶

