- a. During the 3 months after last contact the Coach should:
 - i. Attempt all retention strategies outlined by the retention algorithm (Appendix Z of Manual of Procedures.
 1. For instance, handwritten note, text, call (day, evening, and weekend), email, etc.
 - ii. Note: Families going on a scheduled hiatus are NOT LTF.
- b. Once the family is labeled lost to follow up, Coaches will attempt contact them monthly
- c. A family can come back to the study after being marked LTF.
 - i. When an LTF family comes back, re-engagement will include:
 1. Review of contact info, alt. contacts, and best methods of contact and time of day.
 2. Review of initial motivation for study and link it to why they want to continue.
 3. Problem solving barriers to attendance and make plan for future
 - a. Attempt to rebuild momentum.
 4. Review weight change during break.

Risks to Human Subjects

1. Potential Risks

Safety of human participants is of utmost concern especially in a trial involving children. Efforts will be made to limit the use and disclosure of participants' personal information, including research study and medical or education records, to people who have a need to review this information. We will collect information on changes in height and weight from medical records as needed if a family discontinues study participation or is unable to provide data at the 24-month time point. The assessment process may carry potential risks. For example, some of the questions may be upsetting to participants, and some participants might feel uncomfortable having their height and weight measured. Other risks associated with participation in the intervention include possibly feeling hungry when dieting or sore after exercising. In addition, in select children, excessive attention paid to dieting may lead to an eating disorder or to growth problems. There are also several potential risks to family members in the course of therapy. First, there is a degree of inconvenience for family members who may miss work, school activities, meetings, etc. Second, there is the risk, as there is in any therapy, of a stress reaction occurring. Third, there may be some family disagreements during the implementation of the intervention as issues of family functioning, communication, and discipline may be discussed.

Finally, there is the risk of a breach of confidentiality. Coach interviews are expected to be no or minimal risk of asking the interview questions.

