To account for differences in the frequency of participant contact between the two study groups, blinded measurement staff will systematically assess for AEs in both the intervention and control groups through use of a standardized questionnaire (see MOP) that is administered at each major assessment time point. If any items are endorsed on the questionnaire, the blinded measurement staff will gather additional information and, if necessary, follow the steps for recording and reporting adverse events outlined below and in section **IX.E**. AEs uncovered in the course of treatment will also be subject to the procedures below. Combining between visit and at visit AEs will result in an alternative count that the DSMB requested. This alternative count will be comprised of all AEs, whether reported at or between visits. Blinded coaches will be unaware if an AE was reported between visits, and any duplicates will be removed by an unblinded reviewer (*DSMB Approval, 12.16.2020*)

All AEs, including those not meeting the criteria for SAEs, will be captured on an Adverse Event Form or Serious Adverse Event Form (see **Appendix D**), which must be approved of and signed by the clinical site PI. Information to be collected includes event description, time of onset (and offset if applicable), assessment of severity, relationship to study treatment, expectedness, actions taken,

and outcome of the event. Additionally, all SAEs will require categorization (e.g., death, hospitalization, permanent impairment, etc.) and documentation of any interventions implemented in response to the event.

All AEs occurring during a participant's study participation must be documented appropriately regardless of relationship. All AEs will be followed by the DSMB to adequate resolution and will be recorded in the data collection system. Any medical condition that is present at the time that the participant is screened will be considered as baseline and not reported as an AE. However, if the study participant's condition deteriorates at any time during the study, it will be recorded as an AE. Changes in the severity of an AE will be documented to allow for an assessment of the duration of the event at each level of severity. AEs characterized as intermittent require documentation of onset and duration of each episode.

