Adverse event questionnaires and reporting forms are included in Appendix D of the study protocol. Once a site's research staff becomes aware of an adverse event's occurrence, that staff (i.e., PLAN coach or assessor) will consult with the clinical site PI or project coordinator to complete the appropriate event form and notify the SMC. Adverse event questionnaires will only be administered after assessment measurement by blinded measurement staff, who will correspondingly complete an adverse event log (10.12.20; *DSMB approval, 12.16.2020*). The SMC will then evaluate the severity of the event and determine the necessity for immediate action on behalf of the study group. If immediate action is necessary, the SMC will consult with the Steering Committee to recommend a course of action (e.g., discontinuation of treatment, referral to higher level care). If immediate action is not necessary, the event will be documented in the study database and discussed at the next scheduled DSMB meeting. Additionally, the DCC will prepare monthly reports that summarize adverse events and assess whether there is evidence of a between group difference in AE and SAE rates.

All adverse events and study withdrawals, together with a detailed explanation of the event and withdrawal, will be forwarded to the DCC and the DSMB. In addition, at its regular meeting, the DSMB will summarize all adverse events of any severity, to be forwarded to the IRB via the designated PI. All serious adverse events will be immediately recorded by the clinical site PI and reported to the IRB and DCC, via the designated PI; information (i.e., event, actions, and implications for study) will then be distributed to the other clinical sites. Any SAEs and AEs that are judged to be possibly or probably related to participation in the study and/or change their assessment of risk of participation will be immediately reported to the DSMB. The remaining SAE/AEs will be sent to the DSMB with the 6 month reports (***DSMB approved protocol addenda, 3.18.19***). If any participant appears to be in crisis but the event is not classified as an SAE, appropriate action will be taken based on established suicide and crisis protocols, and any adverse event will be reported promptly to the DSMB and IRB.

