Non-fatal, non-life-threatening unexpected, suspected serious adverse event	Within 15 calendar days of initial receipt of information	Contact PI	
 • IRB of Record • NHLBI • SMC • DCC • All PIs and Co-Is
		Clinical Site PIs	
 • Internal IRBs
Unanticipated problem that is not an SAE	Within 14 days of the investigator becoming aware of the problem	Contact PI	
 • IRB of Record • NHLBI • SMC • DCC • All PIs and Co-Is
		Clinical Site PIs	
 • Internal IRBs
All unanticipated problems	Within 30 days of the IRB's receipt of the report of the UP from the investigator.	IRB	
 • OHRP
		Contact PI	
 • IRB of Record
		Clinical Site PIs	
 • Internal IRBs
All non-serious AEs that are not UPs	Documented in study database and reported annually	Contact PI	
 • IRB of Record
		Clinical Site PIs	
 • Internal IRBs

Study Halting Rules for Participant Safety

There are few risks to family-based behavioral interventions. The intervention focuses on improving child and parent health behaviors through behavioral strategies and improved parenting and parent/child relations. The main risks are development of disordered eating or psychopathology and risks due to a sedentary person beginning to exercise. We will be carefully monitoring participants for excess weight loss, psychopathology, and activity-induced injuries. Although we expect that there will be very few serious adverse events, we will employ the following stopping guideline based on the number of SAEs in the intervention group. The guideline is summarized in **Table 11**, which provides data for maximum acceptable SAE rates of 2%, 4%, 6%, 8%, and 10% and for observed numbers of SAEs of 2, 3, 4, and 5. **Table 11** is calculated using 1-sided 95% binomial confidence intervals and can be interpreted as presenting the maximum total sample size N that is required in order to conclude that the toxicity level of the intervention may be excessive for a given number of

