The DCC will organize annual site visits to all clinics that will focus on a detailed review of study procedures. Special additional site visits may occur if routine quality control measures determine that a clinic is having difficulty with some aspect of the protocol. Site visitors will prepare an agenda that will include observations of the performance of study procedures and of the filing system that is used to store completed data forms. They will confirm that data forms are correctly filed, that IRB approvals are available, and that changes on forms are appropriately initialed and dated by the person who made the changes. In addition, site visitors may do random data audits in accordance with section **X.F.2**. Site visits will generally be conducted by a DCC staff person and by an investigator from another clinic.

III. Statistical Considerations

A. Statistical Analysis Plan

Data will be analyzed with SAS using the intention-to-treat principle. P-values less than 0.05 will be considered significant and all tests are two-sided. Details of how the intention-to-treat principle will be implemented are contained in a later section.

B. Primary Analysis

The primary goal of this study is to determine whether the change in weight status among children who have overweight/obesity (*Primary Specific Aim 1, DSMB approved protocol addenda, 11.2.18*) is superior among those who are randomized to family-based treatment (FBT) as compared to those who are randomized to usual care (UC) when treated in a primary care setting. The primary outcome measure in children is the percent over the age- and sex-specific 50th BMI percentile. The specific question of interest in the primary analysis is whether the change from baseline to 24 months in the intervention group is greater in the FBT group than in the UC group.

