The primary analysis will be an intention-to-treat analysis of the child that includes all subjects. Recalling that the primary analysis involves an analysis of covariance with the 24-month value of percent over BMI (the primary outcome measure) as the dependent variable, the inclusion of all subjects will reflect the following three considerations.

1. If the 24-month value of the primary outcome is available, the child will be included in the primary analysis without the need for further considerations.
2. If the 24-month value of height and/or weight (the defining components of the primary outcome) is missing and the child had height and weight data collected by his or her pediatrician at a clinic visit that occurred within 30 days of the targeted 24-month PLAN assessment, the following considerations will be used in imputing the 24-month value to be used in the primary analysis. Those considerations are designed to account for the anticipated imprecision of values measured at the pediatrician's office.
 - a. Within each clinic, a regression model that will allow us to impute 24-month values will be generated. Using all PLAN children who attend a particular clinic and who have both precisely measured PLAN height and weight data and less precise height and weight data measured at the clinic within 30 days of the PLAN measurement, clinic-specific regression models will separately predict the true height and weight using the age and sex of the subject as well as the height and weight value measured at the clinic. The goal will be to perform these calculations on a clinic-specific basis because the causes and magnitude of measurement error may differ

from clinic to clinic. However, if the number of subjects at a clinic who have the requisite height and weight data is less than 15 (less than 5 times the number of predictors), we will use all data from all clinics at the relevant study site to perform the desired imputation.

- b. Recalling that the children of interest in this scenario have clinic data collected within 30 days of the targeted 24-month PLAN assessment, the clinic-specific height and weight value calculated above will be used to impute the PLAN 24 month values from the contemporaneous value measured at the clinic. This imputed value will be used in the primary analysis.

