1. Strongly Agree
2. Agree
3. Neither Agree or Disagree
4. Disagree
5. Strongly Disagree

The content of FBT is clear.

1. Strongly Agree
2. Agree
3. Neither Agree or Disagree

4. Disagree
5. Strongly Disagree

FBT can be implemented without requiring an extensive training.

1. Strongly Agree
2. Agree
3. Neither Agree or Disagree
4. Disagree
5. Strongly Disagree

FBT can be adapted or modified to suit the needs of the interventionist.

1. Strongly Agree
2. Agree
3. Neither Agree or Disagree
4. Disagree
5. Strongly Disagree

The benefits of using FBT with my clients are obvious/visible.

1. Strongly Agree
2. Agree
3. Neither Agree or Disagree
4. Disagree
5. Strongly Disagree

The evidence regarding the impact of FBT is available.

1. Strongly Agree
2. Agree
3. Neither Agree or Disagree
4. Disagree
5. Strongly Disagree

The content of FBT is relevant to my work as a clinical treatment provider.

1. Strongly Agree
2. Agree
3. Neither Agree or Disagree
4. Disagree
5. Strongly Disagree

Coach consent

Please upload the .pdf file of the signed Coach consent.

Indicate yes or no that Coach consent is uploaded.

[figure not shown]
- No

- Yes

Why is the coach consent not uploaded? _____

D. Additional Forms

Figure 1. Study Flow Chart

PLAN Adverse Event Questionnaire

During the time since your last visit on (*insert date of last major assessment*), have you or your child:

1. Been hospitalized overnight?

YES NO

2. Been to the emergency room or an urgent care clinic?

YES NO

3. Been treated by a medical provider for illness or injury?

YES NO

4. Had any injuries (e.g., sprained ankle or broken bone)?

YES NO

5. Started any new medications or receive a change in dosage of a current medication?

YES NO

6. Experience increased symptoms of a current illness or injury (If applicable)?

YES NO

7. Seen a new counselor, psychologist, or psychiatrist?

YES NO

8. Gone long periods (8 waking hours or more) without eating to control your weight?

YES NO

9. Felt like you have lost control over your eating?

YES NO

10. Thrown up after eating?

YES NO

11. Taken laxatives or diet pills?

YES NO

12. Felt particularly nervous, worried, or anxious?

YES NO

13. Felt very sad or down? Or lost interest in things that you normally enjoy doing?

YES NO

(This change was made on 5.23.18 prior to review and approval by the DSMB, DSMB approved protocol addenda on 11.2.18)

ADVERSE EVENT FORM

The Effectiveness of Family-based Weight Loss Treatment Implemented in Primary Care

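### Growth problems and eating disorders are named as possible child harms, but no by-arm analysis of either is specified, and growth has no adverse-event category or questionnaire item

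*Combined protocol and SAP*

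**What the plan says.** **Named harms.** Under Risks to Human Subjects, Potential Risks, the protocol states that "in select children, excessive attention paid to dieting may lead to an eating disorder or to growth problems". The halting-rules section adds: "We will be carefully monitoring participants for excess weight loss, psychopathology, and activity-induced injuries". Growth is not in that list.

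**Height.** The Assessments section says "Child height will also be measured at each major assessment or as needed to determine progress", and Table 4 marks height and weight at 0, 6, 12, 18 and 24 months. In the statistical section, height serves only to form the outcome: "The primary outcome measure in children is the percent over the age- and sex-specific 50th BMI percentile".

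**Adverse events.** The tracking section says that "blinded measurement staff will systematically assess for AEs in both the intervention and control groups through use of a standardized questionnaire". Table 4 places this survey at 6, 12, 18 and 24 months, not at baseline. Items 8 to 11 of the questionnaire cover fasting ("Gone long periods (8 waking hours or more) without eating to control your weight"), loss of control over eating, vomiting, and laxatives or diet pills. Each is one yes/no answer covering parent and child together. Table 8 lists new eating disorders, and loss of control without an external cause, as expected and possibly related events.

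**Comparison by arm.** The coordinating center's monthly reports are to "assess whether there is evidence of a between group difference in AE and SAE rates". The numeric guideline in Table 11 counts SAEs in the FBT arm only.

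**Removal from analysis.** Participant Withdrawal or Termination allows participants with unhealthy weight loss or concerning disordered-eating symptoms to be taken out of the research analyses, as decided by the executive and safety committees and the DSMB.

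**The concern.** FBT sets calorie ranges for children aged 6 to 12 over two years. The protocol itself says that dieting may harm growth or eating behavior in some of them, and the trial collects data in both randomized arms that bear on both harms. Yet the statistical section, from the primary analysis to Exploratory Aim 2, contains no growth outcome, no disordered-eating outcome and no safety comparison. A favorable primary result could therefore be published without a prespecified statement on linear growth. The primary outcome cannot fill that gap, because excess weight loss scores as benefit and slowed growth can leave the score unchanged. The withdrawal provision makes this worse: it could remove the affected children, and FBT families have more contact in which symptoms can be noticed.

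**Working it through.** **1. The plan's only numeric safety rule.** Table 11 gives the largest n for which the one-sided binomial tail P(X ≥ r | n, p) is at most 0.05. For r = 3 and p = 2%, the tail is 0.0486 at n = 41 and 0.0515 at n = 42, so the stated 41 is right. All 20 cells reproduce. The rule is sound for SAEs in FBT, but it compares no arms and does not address growth.

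**2. Tracing each harm through the plan.**

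| | Growth problems | Eating disorder |
|---|---|---|
| Named as a risk | yes | yes |
| Tables 8 and 9 | absent | new eating disorder; loss of control |
| AE questionnaire | no item | items 8 to 11, parent and child pooled |
| Data in both arms | height at five visits | questionnaire at four visits |
| Harm-specific analysis by arm | none | none |

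**3. Percent over BMI and growth.** Take an illustrative child of 135 cm and 45 kg: BMI = 45/1.35² = 24.7. Two possible outcomes at the same later age:
- 147 cm and 50.0 kg: 50.0/1.47² = 23.1
- 143 cm and 47.3 kg: 47.3/1.43² = 23.1

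Age and sex are the same, so the 50th-percentile reference and the outcome are the same. A 4 cm shortfall in height does not show.

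**4. What a height analysis could exclude.** From the documents: 528 families, 1:1, so 264 per arm; 20% dropout leaves 264 × 0.8 ≈ 211. Assumed, because the documents give no figure: SD of 24-month change in height z-score of 0.3 to 0.6.
- Half-width without clustering = 1.96 × SD × √(2/n). At n = 264 this is 0.05 to 0.10; at n = 211 it is 0.06 to 0.11.
- With 12 coaches in FBT, m = 211/12 = 17.6 children per coach. At ICC 0.04, the lowest value in the power table, the design effect is 1 + 16.6 × 0.04 = 1.66. Half-width = 1.96 × SD × √((1.66 + 1)/211) = 0.07 to 0.13.
- At ICC 0.15, the highest tabulated, the design effect is 1 + 16.6 × 0.15 = 3.49, and the half-width is 0.09 to 0.17.

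These use a normal multiplier, slightly optimistic with 12 coaches. Home-measured heights may also enlarge the SD.

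**5. Mean shift against harm in a few children.** If 2% of children lost 0.5 z (illustration), the mean would move by 0.02 × 0.5 = 0.01, far inside every interval above. A comparison of means alone would not answer the stated risk.

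**6. Disordered-eating items.** The documents give no rates. For assumed child-level rates of 1% vs 4%, 2% vs 6%, 5% vs 10% and 5% vs 12%, a two-sided 5% comparison of proportions, ignoring coach clustering, has power of 51%, 55%, 50% and 73% at 211 per arm (60%, 65%, 59% and 82% at 264). These comparisons are informative with confidence intervals, but are not confirmatory tests.

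**The case against.** The strongest reply is that these harms are handled under the Data Safety and Monitoring Plan, so their absence from the statistical section is partly a matter of location. Every AE is recorded with description, severity, relatedness and outcome, and forwarded to the coordinating center and the DSMB, which summarizes them for the IRB. The AE definition is broad enough to admit a recognized growth problem. That stands, and it rules out three stronger readings.

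- A reader might infer that neither harm would be reported at all. The documents do not support this: new eating disorders and loss of control are listed AEs with a reporting route. What is missing is a harm-specific comparison by arm and, for growth, any prompt to record it.
- A reader might infer that the monthly comparison pools all AEs, so that common childhood illness would hide disordered eating. The text says AE and SAE rates without saying total or by category. Table 8 groups events by type, and Table 9 lists common pediatric events separately. The Manual of Procedures is not available, so a power figure for a pooled test would model a test that the plan does not specify.
- A reader might infer that the trial holds blinded data on both harms. Items 8 to 11 pool parent and child. In Step 1 of the remote protocol, the contacting coach completes the AE survey, which conflicts with blinded collection elsewhere. Remote heights are taken by parents.

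Two further objections also stand. A mean comparison suits a population shift better than harm in select children. A count of children becoming underweight is likely to be near zero, because all start above the 85th BMI percentile. Both shape the fix. Neither supplies a growth analysis.

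**Conclusion.** The concern holds in this form: two child harms are named, no by-arm analysis of either is specified, and growth has no AE category, no questionnaire item and no analysis of the height data. The growth half is the stronger and rests on the documents alone, with simple arithmetic for the BMI example. The eating-disorder half is narrower: cases would be reported individually, but the both-arm questionnaire data have no planned comparison.

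The size can be given only as ranges. Under an assumed SD of 0.3 to 0.6 and 211 children per arm, the trial could bound a mean difference in height z-score to about ±0.06 to ±0.11, or ±0.07 to ±0.13 at coach ICC 0.04. For disordered eating, power is 50% to 73% under the assumed rates. The primary efficacy analysis is not invalidated, except that the withdrawal provision needs reconciling with the intention-to-treat section, which includes all subjects. This should be fixed, and is cheap to fix.

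**What to change.** Add a safety analysis to the statistical section, in all randomized children with available data, regardless of any removal from research analyses under Participant Withdrawal or Termination.

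1. **Growth.** Compare 24-month height-for-age z-score by arm, using the CDC reference already cited, adjusted for baseline height z-score, in the primary partially clustered ANCOVA form, with a 95% confidence interval. Add the by-arm distribution of change in height z, or a count of children with a large fall by a cut-off that the sponsor fixes in advance. Repeat with staff-measured stadiometer heights only.
2. **Disordered eating.** Report child-level answers to items 8 to 11 by arm from the at-visit questionnaire, with confidence intervals. Record whether each positive answer concerns the parent or the child. State that there is no baseline administration.
3. **Underweight.** A by-arm count may be added as a descriptive category chosen by the sponsor.
4. **Reconcile** Step 1 of the remote protocol with the requirement that blinded staff collect AE questionnaires, and report which answers were collected by whom.

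The cost is SAP text, a few tables or models and one form field, with no new visits. Answers already collected without the parent/child field can be separated only where the follow-up detail allows. The downside is a few more estimates, to be labeled as safety summaries and not as hypothesis tests.
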